## 2. STUDY VISIT SCHEDULE

Procedures	Visit 1	Visits 2-16	Visit 17
	BL	Weeks 2-48	Week 52
Informed Consent Procedure	X		
Inclusion/Exclusion Criteria	X		
Brief Medical History and Concomitant Medications Review	X	X	X
Adverse Event Assessment		X	X

Microbiome Collection	X	Week 8, 12	X
Product Dispensing (as needed)	X	X	X
Subject Diary Assessment and Compliance Check		X	X

Subject Product Accountability and Study Completion			X
--	--	--	---

### 3. INTRODUCTION

The etiology of acne is heavily dependent on the production of sebum by the sebaceous glands that results in the growth of the bacteria *c. acnes*. If no sebum is present, there is no nutritional source for the *c. acnes*, the bacteria die, and acne resolves. A newly FDA approved acne medication consisting of clascoterone cream 1% is believed to effectively treat acne due to a decrease in sebum production. This mechanism of action has been postulated based on efficacy observed in the phase III trials that lead to its approval. This research aims to demonstrate the effect of clascoterone cream 1% in sebum reduction.

### 4. STUDY OBJECTIVE

The objectives of this research are as follows:

Primary Efficacy Endpoint: The primary efficacy endpoint is the reduction in causal sebum measurements from the forehead obtained with a sebumeter during the study.

Secondary Efficacy Endpoint: The secondary efficacy endpoint is the changes in the facial microbiome induced by 8, 12, and 52 weeks of clascoterone 1% cream application.

[REDACTED]

[REDACTED]

### 5. STUDY DESIGN OVERVIEW

Female and male subjects will be enrolled in this single site study to evaluate the effect of clascoterone cream [REDACTED] on facial sebum production and acne. Subjects who sign consent and meet all inclusion criteria and none of the exclusion criteria will be enrolled at the baseline visit. Subjects will use their own approved skin care products unchanged for the duration of the study.

At baseline visit, subjects will receive the study product. [REDACTED]

[REDACTED]

[REDACTED] Three casual sebumeter measurements will be taken from the central forehead 2-4 hours after the subjects washed prior to presenting to the research center.

[REDACTED]

[REDACTED]

[REDACTED]

Microbiome swabbing for analysis by [REDACTED] will be obtained from all 40 subjects at baseline, week 8, week 12, and week 52.

## **6. STUDY POPULATION**

### **6.1 POPULATION DESCRIPTION**

Healthy female and male subjects 12+ years of age Fitzpatrick skin types I-VI with mild to moderate acne (10-100 total non-inflammatory lesions (open comedones and closed comedones), 10-50 total inflammatory lesions, no cysts, and up to 2 nodules (if deemed appropriate by the PI) on the face.

### **6.2 POPULATION SIZE**

40 subjects

### **6.3 INCLUSION CRITERIA**

The following items represent the inclusion criteria:

1. Males and females 12+ years of age.
2. Subjects with mild to moderate acne.
3. Subjects must possess 10-100 total non-inflammatory lesions (open comedones and closed comedones), 10-50 total inflammatory lesions, no cysts, and up to 2 nodules (if deemed appropriate by the PI) on the face.
4. Subjects with all Fitzpatrick skin types I-VI.
5. Subjects who agree to use only the study products for acne treatment. No other medicated cleansers or moisturizers or acne treatments of any kind are allowed.
6. Subjects agree not to introduce any new colored cosmetics or skin care products while participating in the study (lipsticks, eye shadows, facial foundations, blush, powder, cleansers, moisturizers).
7. Subjects agree to arrive at all visits with a clean face, having washed his/her face and removed all facial and eye makeup products within 2 hours to 4 hours prior to the visit and is not to use/apply any topical facial product(s) until the visit is completed.
8. No known medical conditions that, in the investigator's opinion, may interfere with study participation.

9. Women of childbearing potential must be willing to use a form of birth control during the study. For the purpose of this study, the following are considered acceptable methods of birth control: oral contraceptives, Norplant®, Depo-Provera®, double barrier methods (e.g., condom and spermicide) and abstinence.
10. Subjects are dependable and able to follow directions and willing to comply with the schedule of visits.
11. Subjects in generally good physical and mental health.
12. Able to read, write, speak, and understand English
13. Individual (and/or his/her legally acceptable representative, as applicable) has signed the Consent for Photograph Release and ICD (and/or Assent Document, as applicable) including Health Insurance Portability and Accountability Act (HIPAA) disclosure.
14. Subject must avoid sun exposure, or use sunscreen if sun exposure is unavoidable.
15. Subject must avoid professional or facial spa procedures during the study.

#### **6.4 EXCLUSION CRITERIA**

The following items represent the exclusion criteria:

1. Any dermatological disorder, which in the investigator's opinion, may interfere with the accurate evaluation of the subject's skin characteristics, except for the study condition of acne.
2. Subjects who are not willing to use the assigned study product to their face as instructed.
3. Subjects who have acne nodules/cysts representative of severe acne.
4. Subjects who are currently using, planning to use during the study or has used any of the following in the specified time range (based on subject report):
  - a. **1 month prior to Visit 1:** Prescription (oral or topically applied on the face) antibiotics, inhaled steroids (except those prescribed for allergies), or hormones (pre- or post-menopausal hormone-replacement therapy; insulin, etc.), or other medications that could make skin more sensitive or have an effect on the skin, as determined by the PI or designee. Oral contraceptives are acceptable.
  - b. **1 month prior to Visit 1:** Prescription medication for acne (e.g. doxycycline, minocycline, clindamycin, sulfamethoxazole and trimethoprim [Bactrim], tetracycline, erythromycin, azithromycin, or Vibramycin®)
  - c. **1 month prior to Visit 1:** Topical prescription retinoids (e.g. Retin-A®, Retin-A Micro®, Renova®, Adapalene, Tazarotene, Avita®, Tazorac®, Avage®, Differin®), azelaic acid, benzoyl peroxide, dapsone, sodium sulfacetamide, Epiduo®, or other similar prescription drug on the face
  - d. **6 months prior to Visit 1:** Accutane or other oral retinoid
  - e. **2 weeks prior to Visit 1:** Any of the following on the face:
    - i. • Light therapy
    - ii. • OTC topical medications/products (including antiacne or

antibacterial agents, topical anti-inflammatories, topical retinoids, etc.). Sunscreens (SPF) are acceptable.

5. Females who are pregnant, lactating, or planning to become pregnant during the study or within 30 days of study completion. (Subject must document her response in either the source documentation or informed consent/assent forms).
6. Subject has a surgery and/or invasive medical procedure planned during the study.
7. Subject has observable suntan, scars, nevi, tattoo, excessive hair (including beard, mustache, or goatee), or other dermal conditions on the face that could interfere with study evaluations or confound study results, as determined by the PI or designee.
8. Subject is taking medications that would mask an adverse event (AE) or influence the study results, including:
  - a. Immunosuppressive drugs and steroidal and/or non-steroidal anti-inflammatory drugs within 3 months before Visit 1 and during the study.
  - b. Regular use of antihistamines within 1 month before Visit 1 and during the study.
9. Subject has a history of or a concurrent health condition/situation, which in the opinion of the PI, if medically qualified, or Study Physician, may put the individual at significant risk, confound the study results, or interfere significantly with the individual's participation in the study.
10. Subject is an employee/contractor or immediate family member of the PI, Study Site, or Sponsor.
11. Subjects with clinically significant unstable medical disorders.
12. Subjects who are unwilling or unable to comply with the requirements of the protocol.
13. Subjects with any known allergies or sensitivities to the study acne products.
14. Subjects who are currently under the care of a dermatologist for acne.
15. Subjects who are currently experiencing an acne flare.
16. Subjects who have history of a psychological illness or condition that would interfere with their ability to understand and follow the requirements of the study.
17. Subjects having started hormone replacement therapies (HRT) or hormones for birth control less than 3 months prior to the study entry or who plan on starting, stopping or changing doses of HRT or hormones for birth control during the study.

## **6.5 CONCOMITANT MEDICATIONS**

All oral prescription medications should remain unchanged during the study. No topical medications of any kind can be used on the face. Subjects must use their own self-selected skin care products during the study that they have used without problems for the past 30 days.

## 7. CONDUCT OF STUDY: METHODS AND PROCEDURES

### 7.1 ENROLLMENT

#### 7.1.1 INFORMED CONSENT

A signed informed consent form must be obtained from each subject prior to performing any study procedures. No study related procedures or activities will be performed until each subject is fully informed and the consent form is signed and dated.

#### 7.1.2 DERMATOLOGICAL EXAMINATION

A dermatological examination will be performed.

#### 7.1.3 STUDY PROCEDURES

The subjects will be screened for the inclusion and exclusion criteria prior to study enrollment. Only subjects who meet the requirements, have signed an informed consent, and have given a medical history will be entered into the study. All other subjects will be considered screening failures.

#### 7.1.4 STUDY MATERIAL ADMINISTRATION

All subjects will use clascoterone cream 1% to the face twice daily.

#### 7.1.5 SCREENING PROCEDURES

Potential volunteers will be enrolled based on their ability to meet the inclusion/exclusion criteria required for study enrollment.

### 7.2 STUDY CONDUCT PROCEDURES

#### 7.2.1 BASELINE

Female and male subjects will be enrolled in this single site study to evaluate the effect of clascoterone cream [REDACTED] on facial sebum production and acne. Subjects who sign consent and meet all inclusion criteria and none of the exclusion criteria will be enrolled at the baseline visit. Subjects will use their own approved skin care products unchanged for the duration of the study.

At baseline visit, subjects will receive the study product. The dermatologist investigator will assess facial appearance in terms of oily appearance, pore size, and facial shine. [REDACTED]

[REDACTED]  
[REDACTED]  
[REDACTED]  
[REDACTED] Three casual sebumeter measurements will be taken from the central forehead 2-4 hours

after the subjects washed prior to presenting to the research center. A microbiome sample will be taken from the cheek.

[REDACTED]

7.2.2 WEEK 2, WEEK 4, WEEK 6, WEEK 8, WEEK 10, WEEK 12, WEEK 16, WEEK 20, WEEK 24, WEEK 28, WEEK 32, WEEK 36, WEEK 40, WEEK 44, WEEK 48, WEEK 52

Subjects will return to the research center at Week 2, Week 4, Week 6, Week 8, Week 10, Week 12, Week 16, Week 20, Week 24, Week 28, Week 32, Week 36, Week 40, Week 44, Week 48, Week 52 for the same assessments as performed at baseline. Old study product and diaries will be collected and new diaries and study product dispensed as needed at each visit. Subjects will continue participation for 52 weeks, at which time their study participation will be completed.

Microbiome sampling will occur at weeks 8, 12, and 52.

## 8. EFFICACY MEASURES

### 8.1 STUDY MEASURES

[REDACTED]

[REDACTED]

[REDACTED]

[REDACTED]

[REDACTED]

[REDACTED]

Sebumeter measurements: 3 sebumeter measurements will be taken from the forehead 2-4 hours after facial washing at each study visit.

Microbiome assessment: Swabbing of the cheek for microbiome analysis will be performed from all subjects at baseline, week 8, week 12, and week 52.

## **8.2 SUBJECT COMPLIANCE**

Compliance will be determined from the diary sheets. Subjects will record product application and any comments on the provided weekly diary. Diary sheets will remain at the study center as part of the source documentation records.

## **8.3 NONCOMPLIANT SUBJECTS**

Subjects who are found to be noncompliance will be queried as to the reason for their noncompliance. If noncompliance results from study product problems, a full interview will be conducted by the investigator to determine the nature and severity of the problem and an adverse event will be recorded. Subjects who are noncompliant will be released from their study participation and their last visit will be carried forward in the data analysis.

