**1. PROTOCOL SYNOPSIS**

Title of Study:	Clinical Evaluation of the Sebum Reduction Induced by Clascoterone Cream 1%
Study Period:	52 weeks (Baseline, Week 2, Week 4, Week 6, Week 8, Week 10, Week 12, Week 16, Week 20, Week 24, Week 28, Week 32, Week 36, Week 40, Week 44, Week 48, Week 52)
Test Products	Winlevi (Clascoterone Cream 1.0%) Applied to entire face morning and evening.
Objective:	
The objectives of this research are as follows:
 
 
1. The primary objective is to assess the ability of clascoterone cream 1% to reduce casual facial sebum at weeks 4, 8, 12, 16, 20, 24, 28, 32, 36, 40, 44, 48, and 52.
 
2. The secondary objective is to assess the ability of clascoterone cream 1% to reduce casual facial sebum at weeks 2, 6, and 10.
 
3. The tertiary objective is to demonstrate microbiome changes after 8, 12, and 52 weeks of clascoterone 1.0% facial application.
 

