### **9.1 COMPLETED, DISCONTINUED OR INCOMPLETE SUBJECTS**

A completed subject is a subject who has satisfied all study entry criteria and completed the 52-week study. For any subject who has started study and terminates the study prematurely, every effort will be made to obtain final evaluations of clinical status. Reasonable effort will be made to contact any subject lost to follow-up during the course of the study in order to complete assessments and retrieve any outstanding data and clinical supplies. The investigator will choose the description that best describes the status of the subject at termination.

1. Subject completed the 52-week study period

OR INCOMPLETE/DISCONTINUED DUE TO:

2. Contact dermatitis
3. Adverse experience
4. Serious adverse experience
5. Pregnancy
6. Protocol violation
7. Subject withdrew consent
8. Subject lost to follow-up
9. Other

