## **12. STATISTICAL METHODS**

Along with descriptive statistics (means, standard deviations and percentages), investigator and subject ordinal nonparametric data will be analyzed using the Wilcoxon signed rank test. Change will be considered significant at a p value less than or equal to 0.05. [REDACTED]

[REDACTED] sebumeter measurements will be assessed with a Student's t test again with significance at a p value less than or equal to 0.05.

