## **12.5 ENDPOINTS**

### **12.5.1 PRIMARY EFFICACY ENDPOINT**

The primary efficacy endpoint is the reduction in causal sebum measurements from the forehead obtained with a sebumeter during the study.

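### Releasing noncompliant subjects and carrying their last visit forward lets early sebum readings count as late ones, and can overstate the sustained reduction through Week 52

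*Combined protocol and SAP*

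**What the plan says.** Section 8.3 sets the rule: "Subjects who are noncompliant will be released from their study participation and their last visit will be carried forward in the data analysis". Section 8.2 says how noncompliance is found: "Compliance will be determined from the diary sheets". No threshold is visible. Section 7.2.2 says when the diaries reach the site: "Old study product and diaries will be collected and new diaries and study product dispensed as needed at each visit".

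For early termination, section 9.1 promises that "every effort will be made to obtain final evaluations of clinical status", but it schedules no further visits up to Week 52.

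The primary endpoint in section 12.5.1 names no single time point: "The primary efficacy endpoint is the reduction in causal sebum measurements from the forehead obtained with a sebumeter during the study". The synopsis supplies the time points, since the primary objective is to "reduce casual facial sebum at weeks 4, 8, 12, 16, 20, 24, 28, 32, 36, 40, 44, 48, and 52". Section 12 gives the test: "sebumeter measurements will be assessed with a Student's t test again with significance at a p value less than or equal to 0.05". Section 12.2 makes it two-sided. Section 10.6 confirms that every subject receives the same product, and section 6.2 sets 40 subjects.

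Parts of the document are redacted. In the visible text, carry-forward is the only missing-data rule. No estimand, no sensitivity analysis and no rule for subjects who leave for other reasons can be seen.

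**The concern.** The rule first ends follow-up of people who might have kept attending, so the protocol itself creates the missing data. It then fills the gap with an old value that the t test treats as observed. A subject whose last visit is Week 4 would have that one reading counted at Week 4 and at the other 12 primary time points (13 − 1), Week 52 included.

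The question at those later visits is whether the reduction lasts, and carrying an early value forward assumes that it does. A control arm handled in the same way might absorb some of the distortion, but this study has none. Section 8.3 also expects some noncompliance to come from problems with the product, so who is released may depend on how treatment is going.

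**Working it through.** The plan gives no figure to reproduce. Section 12.1 says only that the sponsor chose 40 subjects, with no effect size, SD or dropout rate.

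**Inputs from the documents:** n = 40; 13 primary time points from Week 4 to Week 52; two-sided 0.05, hence 2.5% in the direction of a reduction; one arm. The t test is taken as paired, on change from baseline.

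**Inputs assumed, because the documents are silent:**
- f, the share released: 5%, 10%, 20% or 30%, that is 2, 4, 8 or 12 of 40.
- r, the effect present at a released subject's last visit, as a fraction of the completers' Week 52 reduction.
- ρ, the effect truly present in that subject at Week 52, as the same fraction.

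**Step 1: bias in the mean.** Set the completers' reduction to 1.

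- Mean with carry-forward = (1 − f) + f·r
- Actual mean in all enrolled = (1 − f) + f·ρ
- Bias = f·(r − ρ)
- Overstatement factor = [(1 − f) + f·r] / [(1 − f) + f·ρ]

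| Case | f = 5% | 10% | 20% | 30% |
|---|---|---|---|---|
| Full effect carried, full return to baseline (r = 1, ρ = 0): 1/(1 − f) | 1.05 | 1.11 | 1.25 | 1.43 |
| Full effect carried, half lost (r = 1, ρ = 0.5): 1/(1 − 0.5f) | 1.03 | 1.05 | 1.11 | 1.18 |
| Half effect carried, full return (r = 0.5, ρ = 0): (1 − 0.5f)/(1 − f) | 1.03 | 1.06 | 1.13 | 1.21 |
| Carried value equals the later state (r = ρ) | 1 | 1 | 1 | 1 |
| Half effect carried, target is everyone still on cream (r = 0.5, ρ = 1): 1 − 0.5f | 0.975 | 0.95 | 0.90 | 0.85 |

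For example, with f = 20%, r = 1 and ρ = 0, carry-forward gives 1, the actual mean is 0.80, and 1/0.80 = 1.25.

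**Step 2: false claim of a reduction at Week 52.** Suppose nobody has a true change at Week 52, but released subjects carry an early dip of 0.5 to 0.8 SD of the sebum reading. Assume a within-subject correlation of 0.6. The SD of change is then √[2(1 − 0.6)] = 0.894, and its standard error with 40 subjects is 0.894/√40 = 0.141. The carried values shift the mean by f × dip: from 0.05 × 0.5 = 0.025 at the mild end to 0.30 × 0.8 = 0.24 at the severe end. Simulating the paired t test with n = 40 gives:

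| Share released | Chance of a significant reduction (nominal 2.5%) |
|---|---|
| 5% | about 3–4% |
| 10% | about 5–7% |
| 20% | about 9–17% |
| 30% | about 16–32% |

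The lower end of each range is the 0.5 SD dip and the upper end the 0.8 SD dip.

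**The case against.** The strongest reply is that the direction of bias is not established. A reader might infer that the carried value is a reading taken while the subject was using the cream. The text says only that the last visit is carried. Diaries come back at visits, so noncompliance will often be found at a visit that already falls within the noncompliant period. The final evaluation sought under section 9.1 could also become the carried value. If sebum has already returned to baseline by then, r = ρ = 0 and the bias is nil. Against the effect had everyone stayed on cream, carry-forward of a half-developed effect understates. All of this stands, and it is why the point is worded as *can* overstate.

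Two other strong readings are not supported. One is that the plan runs two incompatible missing-data rules, one for noncompliance and one for other dropouts. Section 9.1 lists other reasons for leaving, but no visible text says how those subjects are analysed. That is a gap, not a second rule. The other is that any missed application counts as noncompliance. The text gives no definition, and an absent threshold is not zero tolerance.

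The largest figures also combine unfavourable assumptions: 30% released, a 0.8 SD dip carried by every released subject, and no true effect at Week 52. At 5% to 10% released the distortion is modest.

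The objection does not rescue the rule itself. In every scenario the plan gives up readings that could have been obtained, treats imputed values as observed and leaves its target undefined. A bias that cannot be signed in advance is a poor property for the primary endpoint.

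**Conclusion.** The concern holds in a conditional form. Following section 8.3 as written allows an early reading to be analysed as a Week 52 result, with no control arm to offset it. That Week 52 is reached is an inference, though a firm one: section 8.3 names no end to the carry-forward, and Week 52 is a primary time point.

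Where a reduction at the last visit is later lost, the sustained effect is overstated. The size ranges from about 5% of the estimate when 2 of 40 are released to about 43% when 12 of 40 are, given a full carried effect and full return to baseline. It is smaller for partial return, zero when the carried and true values agree, and reversed against an always-on-cream target. The release rate and the course of sebum after stopping are unknown, so these figures show what could happen and are not forecasts.

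The change is worth making before data are collected, because readings not taken after release cannot be recovered by reanalysis.

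**What to change.** 1. **Section 8.3.** Replace release and carry-forward with continued sebum measurement at the scheduled visits where consent allows. Leave any decision on product use to the investigator.
2. **Target.** State that the primary analysis estimates the change from baseline in all enrolled subjects, whatever their compliance. State also how subjects who leave for other reasons are handled.
3. **Section 12.** Replace the separate t tests with one repeated-measures mixed model on all observed sebum values. Fit visit, including baseline, as a factor and take each visit-minus-baseline contrast from the model. Visits are 2 weeks apart to Week 12 and 4 weeks apart afterwards, so the covariance must respect unequal spacing. A random subject effect plus continuous-time (spatial-power) errors, with Kenward–Roger degrees of freedom, is one suitable choice. An unstructured matrix over 17 visits would need 17 × 18/2 = 153 parameters, too many for 40 subjects.
4. **Sensitivity.** Add an analysis that sets missing change to zero (return to baseline). It is needed because a model that assumes data missing at random can also project benefit onto people who have left. Keep carry-forward at most as a further sensitivity analysis.
5. **Reporting.** Give the number of missing values at each visit.

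The cost is protocol wording, a few retained visits on the existing schedule and slightly more analysis work. The estimated reduction may come out smaller. No extra subjects or procedures are needed.
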